10.8 Case Report Forms and Source Documents

10.8.1 Case Report Forms

The sponsor or designee will supply eCRFs for each enrolled patient will be provided and historical information and study data, which are specified by the protocol, will be recorded on eCRFs by the investigator. All patient data from study visits must be

collected on source documents and promptly entered in the eCRFs in accordance with the specific instructions given. eCRF entries will be performed by an investigator, subinvestigator, and study coordinator(s) with written authorization. Data should be entered within 3 days after each patient's visit.

When queries are generated to the study center for resolution by the sponsor or designee, eCRF data will be corrected or a response will be recorded in accordance with the specific instructions given. The investigator must ensure that data reported in the eCRF is accurate, complete, legible, and timely and sign the eCRFs to verify the integrity of the data recorded.

A list of the reference ranges for all laboratory tests to be undertaken will be collected prior to the initiation of the study. The list of reference ranges for all laboratory tests should be updated if they are changed during the study. If a central laboratory has been selected to perform any or all tests, it is essential that the reference ranges for all laboratory tests to be performed at the laboratory should also be collected.

10.8.2 Source Data and Source Documents

Source documentation supporting the eCRF data should indicate the patient's participation in the study and should document the dates and details of study procedures, AEs, and patient status. However, the following data will be allowed as data which can be directly recorded in the eCRF:

- Reason for use of prior therapy and/or concomitant therapy
- Severity, seriousness, and causal relationship to the study drug of AE
- Any comments entered in the eCRF

Listed below are the data managed only in the eCRF (ie, items automatically-calculated by the EDC system):

- Age
- BMI
- Respiratory rate (breaths/min)

The investigator must maintain the source documents such as laboratory reports, complete medical history, and physical examination reports. All the source documents must be made accessible for verification by the site monitor(s), auditor(s), the IRB/IEC, regulatory authority inspector(s). Direct access to these documents must be guaranteed by the investigator, subinvestigator, or study coordinator, who must provide support at all times for these activities. For all sources of original data required to complete the eCRFs, the sponsor and the site staff must thoroughly understand the nature and location of the source documents. If electronic records are maintained at the study center, the method of verification must be specified in document within the study center.

10.8.3 External Data

The following data will be reported in separate documents from the eCRFs.

- Plasma concentrations of S-033447 (determined according to procedures specified in a separate document)
- Results of virology tests (determined according to procedures specified in a separate document)
- Safety laboratory test

10.9 Committees

10.9.1 Independent Data Monitoring Committee

No independent data monitoring committee will be established for this study.

10.10 Termination or Suspension of the Study

10.10.1 Termination or Suspension of the Entire Study

The sponsor may prematurely terminate or suspend the study at any time for the following reasons:

- Ensuring safety of the study is difficult due to safety concerns (eg, occurrence of many serious treatment-related AEs)
- Achieving the purpose of the study is considered impossible (eg, inadequate recruitment of patients)

If the study is prematurely terminated or suspended, the sponsor should promptly inform the investigators. The investigator or subinvestigator should promptly inform the participating patients and change the study treatment to other appropriate therapy.

For withdrawal criteria for individual patients, see Section 7.8.

10.10.2 Termination or Suspension of the Study by Study Center

The investigator may prematurely terminate or suspend the study in the study center with agreement of the sponsor at any time when the investigator considers that ensuring safety of the study is difficult due to safety concerns (eg, occurrence of many SAEs).

The sponsor may request the investigator to prematurely terminate or suspend the study in the study center at any time when major violations/deviations of protocol, other procedures, and ICH GCP guidelines were not improved.

If the study is prematurely terminated or suspended, the investigator or subinvestigator should promptly inform the corresponding IRB/IEC and participating patients and change the study treatment to other appropriate therapy(ies).

10.11 Protocol Modifications and Deviations

The investigator will conduct the study in compliance with the protocol provided by the sponsor and approved by the IRB/IEC and the regulatory authority(ies). Modifications to the protocol should not be performed without agreement of both the investigator and the

sponsor. Changes to the protocol will require written IRB/IEC approval prior to implementation, except when the modification is needed to eliminate an immediate hazard(s) to the patients.

The investigator or subinvestigator should document any deviation from the protocol and the reason. If the investigator deviates from the protocol or makes a change to the protocol to eliminate an immediate hazard(s) to the patients, the record should be immediately submitted to the sponsor, the study center, and the IRB/IEC by the investigator and the IRB/IEC will provide expedited review and approval. After obtaining approval from the IRB/IEC, the investigator must obtain a written agreement of the sponsor through the study center.

When deviation from the protocol is required to eliminate immediate hazard(s) to the patients, the investigator will contact the sponsor, if circumstances permit, to discuss the planned course of action. Any deviations from the protocol must be fully documented in the source document.

10.12 Data Management

The sponsor will be responsible for data management and analysis. These procedures are specified in a separate document.

10.13 Retention of Data

The study documents must be maintained in accordance with the ICH GCP guidelines and applicable regulatory requirements. The investigator and study center should take measures to prevent accidental or premature destruction of these documents.

If the sponsor is granted manufacturing and marketing approval for the drug, the sponsor will promptly notify the head of the study center in writing.

Records will be retained for either of the following periods, whichever is later:

- Until the approval day of manufacturing/marketing of the study drug or 3 years after the decision to terminate the development is made
- 3 years after the date of discontinuation or completion of the study

However, the duration of retention may be prolonged with agreement with the sponsor. If the investigator withdraws from the responsibility of keeping the study records, custody must be transferred to an appropriate person willing to accept the responsibility.

10.14 Quality Control and Assurance

The sponsor or designee will implement and maintain quality control and quality assurance procedures with written standard operating procedures to ensure that the study is conducted and data are generated, documented, and reported in compliance with the protocol, ICH GCP, and applicable regulatory requirements.

This study will be conducted in accordance with the provisions of the Declaration of

Helsinki and all revisions thereof; in accordance with the ICH GCP, and as required by the applicable regulatory requirements.

The sponsor will provide training necessary for the study to the investigators and the study center personnel prior to the initiation of the study.

10.15 Publication and Disclosure Policy

All information regarding S-033188 provided by the sponsor to the investigator is privileged and confidential and must not be disclosed to any third party. The investigator agrees to use this information to accomplish the study and will not use it for any other purposes without consent from the sponsor. It is understood that there is an obligation to provide the sponsor with complete data obtained during the study. The information obtained from the study will be used for the development of S-033188 and may be disclosed to regulatory authorities, other investigators, corporate partners, or consultants as required.

The sponsor will retain the ownership of all data. All proposed publications based on the study will be subject to the sponsor's approval requirements.

The key design elements of this protocol will be posted in a publicly accessible database.

10.16 Financial Disclosure

The information on financial disclosure for investigators will be addressed in a separate agreement between the sponsor and the investigator.

Appendix 1 Time and Events Schedule

	Treatment Period										Follow-up Period									
	D1	D2	D3	D4	D5	D6	D7	D8	D9	D10	D11	D12	D13	D14	D15	D22 or ET				
Visit Window (days)	V1	V2	V3	OpV1	V4	OpV2			V5						V6	V7				
Informed Consent/Assent	-	-	+1	-	+1	-			±2						±3	±3				
Inclusion/Exclusion Criteria	X																			
Demographics	X																			
Medical History ^a	X																			
Rapid Influenza Diagnostic Test	X ^b																			
Randomization	X																			
Study Drug Dispensation	X																			
Study Drug Administration	X	X	X	X	X															
Body Temperature Measurement	X ^d	4 Times Daily							Twice Daily											
Assessment of Severity of Influenza Symptoms	X ^d				Twice Daily															
Assessment of Health	X ^d								Once Daily											
Assessment of Health Prior to Influenza Symptoms	X ^d																			
EQ-5D-5L	X ^d				Twice Daily											X				
Work Productivity Questionnaire																				
Assessment of Influenza-related Complications (sinusitis, bronchitis, otitis media, pneumonia)	X	X	X	X	X	X			X						X	X				
Full Physical Examination	X ^{e,f}															X ^e				
Symptom-focused Physical Examination		X	X	X	X	X			X						X					
Concomitant Therapies		X	X	X	X	X			X						X	X				
Study Drug Accountability		X	X	X	X	X														
Urine Pregnancy Test(WOCBP) ^g	X				X											X				
Immunological Tests	X ^h																			
Routine Laboratory Tests	X				X										X	X				
Influenza Antibody Titer Test	X ^h															X				

[figure not shown]
Nasopharyngeal (preferred)/pharyngeal (if nasopharyngeal cannot be collected) Swabs (Virology Test)	X ^h	X	X	X	X	X	X	X	X	X	X	X ⁱ	X ^{i,j}
Vital Sign Measurements	X	X	X	X	X	X	X	X	X	X	X	X	X
Electrocardiography	X	X	X	X	X	X	X	X	X	X	X	X	X
Pharmacokinetic Blood Samples	X ^k	X	X ^k	X	X	X	X	X	X	X	X ^k	X	X
Adverse Event Assessment	X	X	X	X	X	X	X	X	X	X	X	X	X
Interview for Meal Consumption	X	X	X	X	X	X	X	X	X	X	X	X	X
Intrahousehold Infection Interview (for Japan only)	X	X	X	X	X	X	X	X	X	X	X	X	X

D = Day, ET = early termination, V = visit, OpV = optional visit.

- a Prior therapies will also be reviewed.
- b Not necessary if a site has performed a Rapid Influenza Diagnostic Test prior to consideration for the study.
- c The patient will measure or assess and record in the patient eDiary, body temperature 4 times daily (morning, noon, evening, and bedtime) from Days 1 to 3 and twice daily (morning and evening) from Days 4 to 14; severity of influenza symptoms twice daily (morning and evening) from Days 1 to 9 and once daily (evening) from Days 10 to 14; assessment of health once daily (evening) from Days 1 to 14; and EQ-5D-5L twice daily (morning and evening) from Days 1 to 9 and once daily (evening) from Days 10 to 14.
- d Predose, if the study treatment is initiated at 18:00 or later on Day 1, the patient will not need to perform Day 1 evening assessments.
- e Body weight will be measured.
- f Height will be measured in the predose examinations only.
- g Urine pregnancy test will be performed only for females who are not diagnosed as postmenopausal.
- h Predose.
- i Virology swabs will be collected if investigator determines that flu symptoms are persisting.
- j Virology swabs will be collected at the early termination.
- k Blood samples will be collected for the measurement of plasma drug concentrations at Visits 2 (Day 2) and 4 (Day 5). If circumstances permit, samples will also be collected at 0.5 to 4 hours post-dose at Visit 1 (Day 1), and at Visit 3 (Day 3) and Visit 6 (Day 15).

Appendix 2 QOL Questionnaire (EuroQol-5 Dimensions–5 Levels)

Appendix 3 Work Productivity (WP) Questionnaire

Work Productivity Questionnaire cover note:

To the investigator:

This questionnaire is designed to capture the impact of influenza symptoms on patients' ability to work and perform normal activities. We would like the patient to complete the questionnaire once, during the clinic visit following resolution of their symptoms

[figure not shown]
1. How many hours or days per week do you work (e.g., full or part time paid work, voluntary work, or studying)?
2. Due to your recent influenza illness, for how many hours or days were you unable to work? ___ hours, or ___ days
3. Due to your recent influenza illness, for how many hours or days did you feel that your symptoms caused you to perform below your normal standard even though you attended work? ___ hours, or ___ days
4. Due to your recent influenza illness, for how many hours or days did you require someone to help you with your normal activities? ___ hours, or ___ days

Appendix 4 Assessment of Health Scale

Health scale

Pre-flu health:

Please circle on the line below **one number** between 0 (worst possible health) and 10 (normal health for someone your age and your health condition) which best describes your pre-flu health.

Appendix 5 Management and Discontinuation Criteria for Abnormal Liver Function Tests

Management and Discontinuation Criteria for Abnormal Liver Function tests have been designed to ensure patient safety and evaluate liver event etiology. (See Guidance for Industry Drug-Induced Liver Injury: Premarketing Clinical Evaluation, FDA: 2009)

1. Abnormal Liver Chemistry Criteria:

The investigator or subinvestigator must review study patient laboratories to identify if any levels meet the following criteria:

- a. AST or ALT $> 5 \times$ ULN
- b. AST or ALT $> 3 \times$ ULN and total bilirubin $> 2 \times$ ULN or PT-INR > 1.5 , if PT-INR is measured.
- c. AST or ALT $> 3 \times$ ULN with signs or symptoms compatible with hepatitis or hypersensitivity (eg, fatigue, nausea, vomiting, right upper quadrant pain or tenderness, jaundice, fever, rash, eosinophilia [$>5\%$])

2. Action to be taken by Investigator:

If any abnormal liver chemistry criterion is met, the investigator or subinvestigator must do the following:

- Patients must be instructed to discontinue study medication immediately.
- Following the initial observed elevation, every effort should be made to have the patient return to the clinic within 72 hours to repeat liver function chemistries and for further hepatic evaluation.
- Every effort should be made to have the patients monitored 2 to 3 times per week until liver function chemistries (ALT, AST, ALP, total bilirubin) resolve, stabilize or return to within the normal range or to baseline levels.
- This event must be reported to the sponsor as soon as possible but no later than 72 hours of learning after its occurrence on the Liver Event Form.
- Consultation with a specialist such as a hepatologist is considered.
- Liver imaging (ie, ultrasound, magnetic resonance imaging (MRI), computerized tomography) is considered.
- For criteria b, the case must be reported as an SAE.

3. Follow-up Examination:

If any of the abnormal liver chemistry criteria are met, the following assessments should be performed at the follow-up visit(s) and documented in the Liver Event Form:

- Clinical symptoms course
- Alcohol use
- Risk factors for nonalcoholic steatohepatitis (NASH) such as diabetes, obesity and hypertriglyceridemia
- Autoimmune hepatitis/cholangitis
- Wilson's disease
- Laboratory Assessments
 - Viral hepatitis serology
 - Hepatitis A IgM antibody
 - Hepatitis B surface antigen (HBs antigen) and Hepatitis B core antibody (HBc antibody)
 - Hepatitis C RNA
 - Hepatitis E IgA antibody
 - Cytomegalovirus IgM antibody
 - Epstein-Barr viral capsid antigen IgM antibody
 - For patients with total bilirubin of $> 1.5 \times \text{ULN}$, conjugated bilirubin should be measured
 - Complete blood count with differential to assess for eosinophilia

4. Restarting Study Medication Criteria

Patients that meet the abnormal liver chemistry criteria may re-start the administration of the study drug, but only if they do not meet the "Drug Discontinuation Criteria Due to Abnormal Liver Chemistry Tests".

Patients with $\text{ALT} > 5 \times \text{ULN}$ to $\leq 8 \times \text{ULN}$ elevations for less than 2 weeks may restart the study drug may at the discretion of the investigator and sponsor if both of the following conditions are met:

- Subsequent liver function chemistries are lower or unchanged
- No signs or symptoms are consistent with hepatitis or hypersensitivity (eg, fatigue, nausea, vomiting, right upper quadrant pain or tenderness, jaundice, fever, rash or eosinophilia [$>5\%$])

All patients that have met abnormal liver chemistry criteria must still be monitored 2 to 3 times per week until liver function chemistries (ALT, AST, alkaline phosphatase, and total bilirubin) resolve, stabilize or return to within the normal range or to baseline levels.

5. Drug Discontinuation Criteria Due to Abnormal Liver Chemistry Tests

Patients must be discontinued from the study as described below:

AST or ALT $> 8 \times \text{ULN}$, confirmed by follow-up testing (ie, initial abnormality is confirmed on subsequent testing), regardless of medical history or physical examination findings

AST or ALT $> 5 \times \text{ULN}$, with elevations for more than 2 weeks or development of

concomitant signs or symptoms consistent with hepatitis or hypersensitivity (eg, fatigue, nausea, vomiting, right upper quadrant pain or tenderness, jaundice, fever, rash or eosinophilia [$>5\%$])

AST or ALT $> 3 \times$ ULN and total bilirubin $> 2 \times$ ULN or PT-INR > 1.5 , if PT-INR measured, confirmed by follow-up testing (ie, initial abnormality is confirmed on subsequent testing), regardless of medical history or physical examination findings.

AST or ALT $> 3 \times$ ULN with signs or symptoms compatible with hepatitis or hypersensitivity (eg, fatigue, nausea, vomiting, right upper quadrant pain or tenderness, jaundice, fever, rash or eosinophilia [$>5\%$]), confirmed by follow-up testing (ie, initial laboratory abnormality is confirmed upon subsequent testing).

AST or ALT $> 5 \times$ ULN and the patient cannot be followed up weekly

Management and Discontinuation Criteria for Abnormal Liver Function Tests (LFT): Algorithm

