5.2 Treatments to be Administered

5.2.1 Patients Aged 20 to 64 Years

Patients who are qualified for entry will be randomly assigned in a ratio of 2:2:1 to receive S-033188, oseltamivir, or placebo according to the assignment procedures specified in Section 5.4. Patients will receive S-033188 or placebo once on Day 1. Oseltamivir or placebo should be dosed 12 hours apart from Day 1 through Day 5. The details of administration are shown in Table 5-1. Study drugs can be taken without regard to food (although food may improve tolerability of oseltamivir).

Patients should be instructed that in the case of missed doses of oseltamivir/placebo they should take the missed dose as soon as they remember, unless it is 2 hours or less before the next dose. They should then continue to take oseltamivir/placebo at the usual times. Patients should not take 2 doses at a time to make up for a missed dose.

Table 5-1 Study Drug Administration (Patients Aged \geq 20 Years)

Treatment Group	Day 1	Day 2	Day 3	Day 4	Day 5*
S-033188					
Oseltamivir placebo S-033188 40 mg (weight < 80 kg)	2 capsules				
S-033188 80 mg (weight \geq 80 kg)	4 tablets				
Oseltamivir					
Oseltamivir 75 mg S-033188 placebo (weight < 80 kg)	2 capsules				
S-033188 placebo (weight \geq 80 kg)	4 tablets				
Placebo					
Oseltamivir placebo S-033188 placebo (weight < 80 kg)	2 capsules				
S-033188 placebo (weight \geq 80 kg)	4 tablets				

* If only 1 dose of oseltamivir or placebo is taken on Day 1 due to the patient being randomized after 17:00, dosing will be completed on Day 6.

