7.6.4.2 Routine Laboratory Tests

Routine hematology, blood chemistry, and urinalysis parameters (Table 7-5) will be measured by the clinical laboratory (see Section 7.6.4.5). Blood and urine samples for routine laboratory tests will be collected at Visit 1 (Day 1), Visit 4 (Day 5), Visit 6 (Day 15) and Visit 7 (Day 22) (or early termination).

Table 7-5 Routine Laboratory Tests

Category	Evaluation items
Hematology tests	Hematocrit, Hemoglobin, Platelet count, Erythrocytes (red blood cells), Leukocytes (white blood cells) with differential (eosinophil count, basophil count, neutrophil count, monocyte count, lymphocyte count)
Blood chemistry tests	Alanine aminotransferase (ALT), Aspartate aminotransferase (AST), Total bilirubin, Direct bilirubin, Indirect bilirubin, Alkaline phosphatase (ALP), Gamma glutamyl transpeptidase (GGT), Lactate dehydrogenase (LDH), BUN, Creatinine, Uric acid, Calcium (Ca), Chloride (Cl), Potassium (K), Sodium (Na), Total protein, Albumin, and C-reactive protein (CRP)
Urinalysis (Qualitative)	Glucose, Occult blood, Protein, and Urobilinogen

The investigator or subinvestigator will assess whether any abnormal changes from baseline (predose at Visit 1, Day 1) are clinically significant (see Section 7.6.5.6).

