7.8 Withdrawal of Patients from the Study or Study Drug

The investigator will make every reasonable attempt to complete the study for each enrolled patient. A patient may withdraw for any reason. The investigator will advise the sponsor about the withdrawal of any patient by the IRT.

The investigator will withdraw a patient from the study or the study drug treatment for any of the following reasons:

- A serious or intolerable AE occurs and the investigator considers that the patient should be withdrawn because of the AE.
- The patient requests to be withdrawn from the study.
- The patient becomes lost to follow-up.
- The investigator determines that the patient should be withdrawn based on the management and discontinuation criteria for abnormal liver function tests (Appendix 5).
- The investigator determines that the patient should be withdrawn because of other reasons.

In the event of a patient's withdrawal, the investigator will promptly notify the sponsor and will make every effort to complete the early termination assessments. All patients withdrawn due to AEs will be followed until resolution of the AEs, until the unresolved AEs are judged by the investigator to have stabilized, or the patient becomes lost to follow-up. The date of completion (for patients who completed the study), date of discontinuation (for patients who discontinued from the study prematurely), period of discontinuation, and reason for discontinuation will be entered in the eCRF. Completion of the study for each patient is defined as the case that the patient completed the follow-up period.

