7.8.1 Clinical Progression or Lack of Response

In cases where on clinical review, patients appear to be deteriorating clinically or have not responded to the study drug, the investigator should consider the possibility of

secondary infections, decompensation of underlying conditions, or progression of influenza. Patients should be assessed, and investigations should be performed as clinically indicated.

In the event an investigator considers that the influenza has not responded and wishes to treat with open-label oseltamivir (not provided by the sponsor), the patient should stop all blinded study drugs. Since unblinding of the study drugs would not alter the management of the patients, unblinding in this situation is discouraged, and the patients should remain in the study for follow-up as described in Section 7.8. Such cases should be discussed urgently with the sponsor or sponsor's designated Medical Monitors.

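### Appendix 5's list for stopping study drug after liver findings is worded as removal from the study, which would end diary and scheduled follow-up for no drug-stopping gain

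*Protocol*

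**What the plan says.** The relevant text is spread over the protocol and the SAP.

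- **Appendix 5, item 2.** At the first elevation meeting any abnormal-chemistry criterion, "Patients must be instructed to discontinue study medication immediately".
- **Appendix 5, item 4.** Such patients "may re-start the administration of the study drug, but only if they do not meet the" drug discontinuation criteria. The list in Section 5 is therefore the test for restarting drug.
- **Appendix 5, Section 5.** Under a heading about drug discontinuation: "Patients must be discontinued from the study as described below". Five criteria follow.
- **Protocol Section 7.8.** "The investigator will withdraw a patient from the study or the study drug treatment for any of the following reasons". The liver bullet in that list begins "The investigator determines that the patient should be withdrawn based on the management" and goes on to cite the discontinuation criteria of Appendix 5. It does not say what the patient is withdrawn from.
- **Protocol Section 7.8.1.** When blinded drug is stopped for non-response and open-label oseltamivir is given, "the patients should remain in the study for follow-up as described in Section 7.8".
- **SAP 6.4 and 9.1.1.1.** A patient without alleviation is censored at the last observation in the primary analysis.

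The flowchart that closes Appendix 5 is not visible in the extracted text, so nothing is inferred from it.

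**The concern.** One list does two jobs. By its heading and by item 4 it is a rule about drug; by its operative sentence it is a rule about staying in the trial. The protocol itself treats these as different things in the title of Section 7.8, and a site that follows the mandatory sentence will take the patient out of the study.

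No provision continues the symptom diary, the remaining scheduled visits or the swabs after study discontinuation. What is at stake is therefore primary-endpoint data, with some virology, in patients who could have supplied it. Two of the criteria can be met through accompanying signs such as fatigue or fever, which are also features of unresolved influenza. Removal under those criteria could thus be linked to not having alleviated, and censoring would then be informative.

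**Working it through.** The plan gives no figure on this point to reproduce. The check sets the passages against each other and then illustrates the loss for one affected patient.

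**1. Does study removal stop any drug that would otherwise continue?** No. Item 2 has already stopped drug at the first elevation, and item 4 bars restarting once a Section 5 criterion is met. Little drug is left in any case:

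- Patients aged 12 to 19 have none after Day 1.
- Adults are due 10 capsules. After the Day 5 morning dose, 10 − 9 = 1 remains. If only one was taken on Day 1, then 10 − 8 = 2 remain; the Table 5-1 footnote provides for this case, "due to the patient being randomized after 17:00, dosing will be completed on Day 6".
- Only a Day 1 or early unscheduled finding leaves more than that.

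**2. When can a criterion be met inside the diary period?** Routine blood is drawn on Days 1, 5, 15 and 22 (Section 7.6.4.2), and the diary ends on Day 14. The Day 1, Day 5 and unscheduled tests therefore matter. Of the five criteria, three need confirmation on retest. The fourth has a limb needing more than 2 weeks of elevation, which falls after Day 14, and a symptom limb with no stated retest. The fifth, for patients who cannot be followed weekly, has no stated retest either.

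**3. Illustrative exit days.** Assume that the 72-hour retest runs from the draw.

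- Day 1 draw: exit about Day 4 (72 h).
- Visit 4 draw (Day 5 or 6): exit from Day 5 (96 h, no retest) to Day 9 (120 + 72 = 192 h).

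These are not bounds. Appendix 5 counts the 72 hours from the observed elevation, and only as a best effort. Laboratory turnaround is not given. Later exits mean smaller losses than those below.

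**4. Diary entries lost.** Symptoms are recorded twice daily to Day 9 and once daily on Days 10 to 14 (Section 7.4.1.2). Days 2 to 14 give 8 × 2 + 5 × 1 = 21 entries. Left after a midday exit:

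- Day 4: 1 + 10 + 5 = 16
- Day 5: 1 + 8 + 5 = 14
- Day 9: 1 + 5 = 6

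**5. Share not yet alleviated, and so censored early.** Protocol Section 9.2 assumes exponential times with medians of 72 h (S-033188) and 100 h (placebo). The planned infected patients number 350 + 62 = 412 and 175 + 31 = 206, in total 618. The share is 2^(−t/median), and the pooled value is (412 × S-033188 share + 206 × placebo share) / 618.

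| t | S-033188 | Placebo | Pooled |
|---|---|---|---|
| 72 h | 0.500 | 0.607 | 0.536 |
| 96 h | 0.397 | 0.514 | 0.436 |
| 192 h | 0.157 | 0.264 | 0.193 |

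At the 84 h median used for oseltamivir in Table 9-1, the shares are 0.552, 0.453 and 0.205. All of these assume that liver events are unrelated to symptom status.

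**6. What early termination still captures.** The Visit 7 column of Appendix 1 doubles as the early-termination visit. Its window is the termination date plus 3 days, and SAP 6.3 uses withdrawal data that fall in a visit window.

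- Exit on Day 5 or 6: early termination can fall as late as Day 8 or 9, inside the Visit 5 window (Days 7 to 11).
- Exit on Day 9: it can reach Day 12, inside the Visit 6 window (Days 12 to 18).
- A swab is taken at early termination. The virus-AUC endpoints need a Day 9 sample (SAP 9.2), so they lose the patient only if that swab falls before Day 7.

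**The case against.** The strongest reply is that this is a slip that sites would read sensibly. The heading and item 4 point to a drug rule, Section 7.8 opens by asking for every reasonable attempt to complete the study, and its liver bullet rests on the investigator's determination. The unseen flowchart may also say plainly which is meant. All of this makes the literal outcome less likely. It does not remove a mandatory sentence, and no visible text corrects it.

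The second reply concerns size, and most of it stands. Liver disorders are an exclusion. Three of the five criteria need confirmation, and two of the four scheduled draws come at or after the end of the diary. Patients who cannot be followed weekly would have compromised follow-up anyway. The SAP has sensitivity analyses (9.1.1.4) that censor discontinued patients at 14 days, including those who stop for an adverse event; results meeting Appendix 5 are recorded as adverse events (Section 7.6.5.6). Re-censoring still cannot recover an alleviation time that was never recorded.

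A reader might infer that Visits 5, 6 and 7 are lost outright after a Day 5 exit. The documents do not support that, because early termination can supply a visit's data. Nor do they support the inference that safety follow-up ends. Early-termination assessments and adverse-event follow-up continue after withdrawal, and Appendix 5 still requires liver monitoring 2 to 3 times per week.

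**Conclusion.** The inconsistency is real and minor. Followed as written, the sentence ends the diary and the uncaptured scheduled follow-up for a patient whose drug has already been stopped, and it censors that patient early if symptoms persist. Context suggests that a drug rule was intended.

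The effect on the trial cannot be computed, because the documents give no rate of liver events, and it is probably very small. A reader might take the pooled shares of 54%, 44% and 19% as evidence of lost power or bias in the primary comparison. They are not. They describe one hypothetical affected patient at assumed exit times under the planning medians, and the number of such patients is unknown. No power loss is claimed. The case for the change is that it costs almost nothing and preserves data from patients who are expected back for liver monitoring anyway.

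**What to change.** Replace the operative sentence in Appendix 5, Section 5 with:

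*Patients must be permanently discontinued from any remaining study drug and should remain in the study for eDiary entries to Day 14 and scheduled visits to Day 22, unless consent is withdrawn or follow-up is not possible.*

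The last clause covers the criterion for patients who cannot be followed weekly. Word the liver bullet in Section 7.8 to match, and the algorithm figure too if it says otherwise. This extends to liver findings the principle that Section 7.8.1 already applies to non-response.

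The cost is one sentence and one bullet, plus the figure if needed. Every liver threshold is unchanged, and no procedures, visits or patients are added.
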